APPENDIX 3. SAS CODE EXAMPLE FOR MULTIPLE IMPUTATION

```
/* First, generate enough data to produce a monotone missing data pattern */
/* MCMC does not work with class statement. Pooled investigator sites and */
/* baseline insulin dose time have been converted to indicator variables */
/* For pooled investigator sites (sitegrln), */
/* let say that x is the total number of */
/* pooled investigator sites. Then, for pooled investigator sites #1, */
/* inv01=1, inv02=0, ..., inv0[x-1]=0 */
/* For pooled investigator sites #2, inv01=0, inv02=1, ..., inv0[x-1]=0 */
/* For pooled investigator sites #[x-1], inv01=0, inv02=0, ..., inv0[x-1]=1 */
/* For pooled investigator sites #x, inv01=0, inv02=0, ..., inv0[x-1]=0 */
/* For baseline insulin dose (strata) time= morning, binstime=1 */
/* For baseline insulin dose time= evening, binstime=0 */
/* No rounding or range is applied for any variable */
/* Non-informative prior is proc mi default MCMC prior information */
/* 200 is proc mi default number of burn-in iterations */

proc mi data = <<insert input dataset name>> out = datamono
    seed =20171220
    NIMPUTE=100;
    by trtpn;
    var inv01 inv02 ... inv0[x-1] binstime HbA1c_BASE HbA1c_WK12 HbA1c_WK18;
    mcmc impute = monotone chain= multiple;
run;

/* Then, do full imputation based on sequential regression models */
/* assuming monotone missing pattern. */
proc mi data = datamono seed = 171016 out = datami NIMPUTE = 1;
    by _imputation_;
    class trtp strata sitegr1;
    var trtp strata sitegr1 HbA1c_BASE HbA1c_WK12 HbA1c_WK18;
    monotone regression;
run;

/* Compute Changes from Baseline and create one categorical variables for */
/* the pooled investigational sites based on the [x-1] indicator pooled */
/* investigational site variables */
data datmichg;
    set datami (in=a drop = HbA1c_WK18 rename = (HbA1c_WK12 = result))
        datami (in=b drop = HbA1c_WK12 rename = (HbA1c_WK18 = result));

    * Visit;
    if a then visit = "Week 12";
    else if b then visit = "Week 18";
```

Document: \sasdata\Mylan\Insulin_glargine\SYA22825\Biostatistics\Documentation\SAP\MYL-1501D-3004_SAP_Final_2_0_clean.doc

Author: [name]

Version Number:

2.0

Version Date:

18OCT2018

Template No: CS_TP_BS016 Revision 4

Reference: CS_WI_BS005

Effective Date: 01Apr2016

Analysis Plan Template

* Change from baseline;
change = result - HbA1c_BASE;

run;

/* MMRM Analysis by _imputation_ */

```
proc sort data=datmichg;
  by _imputation_;
run;
```

```
proc mixed data = datmichg method = REML order=internal;
  by _imputation_;
  class trtp(ref="Process V") strata sitegr1 avisit usubjid;
  model change = HbA1c_BASE trtp strata avisit sitegr1 trtp*avisit / DDFM =
  KR;
  repeated avisit / type = UN subject = usubjid;
  lsmeans trtp*avisit /diff cl;
  ods output diff = lsdiffs(where=(trt= 'Process IV' and _trt='Process V' and
  visit=_visit));
run;
```

```
/* Combine LSmean Differences for Visit 'Week 12' */
proc mianalyze parms(classvar = full) = lsdiffs (where = (visit = 'Week 12'));
  class trtp*avisit;
  modeleffects trtp*pvisit;
run;
```

```
/* Combine LSmean Differences for Visit 'Week 18' */
proc mianalyze parms(classvar = full) = lsdiffs (where = (visit = 'Week 18'));
  class trtp*avisit;
  modeleffects trtp*avisit;
run;
```

Note to programmers: In case of non-convergence or non-estimability issues for the generation of enough data to produce a monotone missing data pattern, replace the two proc mi by the following:

```
proc mi data = impute3 out = datamono seed =20171220 NIMPUTE=100
  round = 1 1 1 1 1 1 1 1 1 1 1 1 1 1 1 1 1 1 1 1
  min   = 0 0 0 0 0 0 0 0 0 0 0 0 0 0 0 0 0 0 0 0
  max   = 1 1 1 1 1 1 1 1 1 1 1 1 1 1 1 1 1 1 1 1;
  var trtpn  binstime inv01 inv02 inv03 inv04 inv05 inv06 inv07 inv08 inv09
inv10 inv11 inv12 inv13 HbA1c_BASE HbA1c_WK12 HbA1c_WK18;
  mcmc impute = monotone chain= multiple /*prior=ridge=p*/;
run;
```

Document:	\sasdata\Mylan\Insulin_glargine\SYA22825\Biostatistics\Documentation\SAP\MYL-1501D-3004_SAP_Final_2_0 clean.doc		
Author:	[name]	Version Number:	2.0
		Version Date:	18OCT2018
Template No:	CS_TP_BS016 Revision 4	Reference:	CS_WI_BS005
Effective Date:	01Apr2016		

Analysis Plan Template

```
proc mi data = datamono seed = 171016 out = datami NIMPUTE = 1;
  by _imputation_;
  class trtp strata sitegr1;
  var trtp strata sitegr1 HbA1c_BASE HbA1c_WK12 HbA1c_WK18;
  monotone regression;
run;
```

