Then, the remaining monotone missing data will be imputed using sequential regression multiple imputation, where a separate regression model is estimated for imputation of each variable (i.e., measurement at each visit) one after the other including the observed values and the values just imputed from the previous visit. Each regression model will include explanatory variables for pooled investigational sites, basal insulin dose time (morning vs. evening), treatment group and all previous (baseline (visit 6), week 12 (visit 12) and week 18 (visit 14)) values of HbA1c.

No rounding or range restrictions will be applied.

Imputed data will consist of 100 imputed datasets. The random seed number for the partial imputation with the MCMC method will be 20171220, and the random seed number for the sequential regression MI will be 171016.

Each of the 100 imputed datasets will be analyzed using the following analysis method. Change from baseline in HbA1c to each post-baseline visit will be calculated based on observed and imputed data. Mean changes from baseline in HbA1c values will be analyzed using a mixed model for repeated measures (MMRM) approach. Restricted maximum likelihood (ReML) estimation will be used. The MMRM model will include the changes from baseline in HbA1c values as dependent variables, the baseline HbA1c values as fixed covariate, pooled investigational sites, basal insulin dose time (morning vs evening), treatment group (MYL 1501D Process V and MYL 1501D Process VI), visit (week 12 and week 18), and treatment group by visit interaction as fixed effects, and subjects as random effect. An unstructured covariance structure will be used to model the within-subject error and the Kenward-Roger approximation will be used to estimate the degrees of freedom. If this analysis fails to converge, the following covariance structures will be tested: AR(1), ARH(1), CS, CSH, TOEP, TOEPH. The covariance structure converging to the best fit, as determined by Akaike's information criteria (AIC) will be used as the primary analysis.

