Treatment group comparison at week 18 will be based on the least square mean (LS mean) difference between treatment groups (i.e., MYL 1501D Process VI – MYL 1501D Process V) in change from baseline in HbA1c estimated by the model in each imputed datasets. Results from analysis of each imputed dataset i.e., LS mean differences and their standard error (SE), will be combined using the Rubin's imputation rules to produced pooled LS mean estimate of treatment difference and its 2-sided 95% confidence interval (CI).

Non-inferiority will be established if the upper limit of the two sided 95%CI for the difference (MYL-1501D Process VI minus Process V) of mean change from baseline to endpoint for HbA1c is not greater than 0.4% at week 18.

Refer to [APPENDIX 3](#) for SAS code example.

For graphical display at scheduled visits, the LS Means and 2-sided 95% CI for the changes from baseline in HbA1c to week 12 and week 18 obtained from the MMRM model will be presented by treatment group. Similar graphical display will be presented for the mean actual HbA1c values and SD over time by treatment group.

Document:	\sasdata\Mylan\Insulin_glargine\SYA22825\Biostatistics\Documentation\SAP\MYL-1501D-3004_SAP_Final_2_0_clean.doc		
Author:	[name]	Version Number:	2.0
		Version Date:	18OCT2018
Template No:	CS_TP_BS016 Revision 4	Reference:	CS_WI_BS005
Effective Date:	01Apr2016		

Analysis Plan Template

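### Does the Appendix 3 example code, with its wrong arm label and its 0-to-1 limits on HbA1c, put the primary analysis at odds with SAP section 16.1.3?

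*SAP*

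**What the plan says.** Section 16.1.3 of SAP V2.0 sets out the primary analysis in prose. The model's arms are "treatment group (MYL 1501D Process V and MYL 1501D Process VI". The quantity tested is the difference "MYL-1501D Process VI minus Process V) of mean change from baseline to endpoint", pooled over 100 imputed datasets by Rubin's rules. On the imputation, the section says: "No rounding or range restrictions will be applied". If the by-arm MCMC step does not converge or is not estimable, a ridge prior and a single model with treatment as a predictor are to be considered.

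The section then points to Appendix 3, headed "SAS CODE EXAMPLE FOR MULTIPLE IMPUTATION". There:

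- The data step builds a variable called `visit` ("if a then visit = 'Week 12"), while the mixed model uses `avisit` and `trtp` ("class trtp(ref='Process V') strata sitegr1 avisit usubjid").
- The filter on the model output goes back to `trt` and `visit` and keeps "where=(trt= 'Process IV' and _trt='Process V' and".
- The Week 12 pooling call names a third variant, `pvisit`.
- The note to programmers gives a replacement PROC MI for the fallback. Its ROUND and MAX lists are all ones and its MIN list all zeros: "max = 1 1 1 1 1 1 1 1 1 1 1 1 1 1 1 1 1 1 1 1". The ridge option is commented out.

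**The concern.** The appendix is the only place where the primary analysis is written as a program, and the prose sends the reader there. Taken literally, the filter passes no Process VI minus Process V difference to the pooling step, so the confirmatory interval could not be produced. In the fallback, limits of 0 and 1 fall on variables measured in percent, with eligibility up to 9.5% at screening. Any HbA1c value imputed under them would be impossible, and the limits contradict both section 16.1.3 and the comment at the top of the same appendix. What would be at stake is pre-specification: if text and code disagree on a non-inferiority analysis, repairs after unblinding could look like choices made with the results in view.

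**Working it through.** No figure in the plan needs reproducing. The check sets the code beside the text and counts.

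**Filter.** Two arms by two visits give 2 × 2 = 4 LS means and 4 × 3 / 2 = 6 pairwise differences. Two of these are wanted (Process VI against Process V at Week 12 and at Week 18). The label Process IV matches none of the 6. The printed program would not get that far, because the data step never creates the `avisit` that the model needs. The second PROC MI also runs by imputation number on data left in treatment order; Appendix 4 has the sort that Appendix 3 lacks. Each slip therefore shows itself as an error or an empty table. None can return a plausible but wrong difference.

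**Fallback lists.** The VAR list holds treatment (1), dose time (1), pool indicators (13) and HbA1c at baseline, Week 12 and Week 18 (3): 1 + 1 + 13 + 3 = 18 variables. The 13 indicators match the 14 pools in section 8.2. The ROUND, MIN and MAX lists each show 20 entries as read from the PDF. By position, entries 16 to 18 fall on HbA1c. How SAS treats 20 entries for 18 variables was not tested, so whether values would be forced into 0–1 or the step would stop is unknown.

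**Reach of the fallback.** Three things must coincide:

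1. The by-arm MCMC step must fail to converge or be non-estimable.
2. A subject must have a gap before an observed value, since the comment in Appendix 4 confirms that this step fills holes and leaves end-of-study dropouts for the regression step, which has no limits. Baseline gaps are unlikely, because section 7.2 takes the last non-missing pre-treatment value, unscheduled ones included. That leaves Week 12 missing with Week 18 observed. The rescue rule in section 16.1.2 blanks Week 18, not Week 12, so it creates no such gaps.
3. No unscheduled HbA1c may fall in the Week 12 window of section 7.4 (days 76 to 91).

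The pools in section 8.2 sum to 13 + 9 + 13 + 19 + 16 + 9 + 10 + 12 + 29 + 37 + 13 + 8 + 23 + 8 = 219 subjects. If 1% to 5% had such a gap (assumed; the documents give no rate), that is 0.01 × 219 = 2.2 to 0.05 × 219 = 11.0 subjects. Their own Week 18 value is observed. A bad Week 12 value could reach the Week 18 contrast only indirectly, through the imputation regression for other subjects and the visit covariance.

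**Random effect.** Section 16.1.3 also mentions subject as a random effect, while the V2.0 code has only a REPEATED statement with unstructured covariance. With two visits that covariance has 2 × 3 / 2 = 3 free parameters, and a random intercept adds nothing they do not already cover. This too is a difference of wording.

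**The case for a change.** The best argument for a correction is that this is more than a loose template. The fallback names a specific dataset and spells out all 13 indicators, so it reads as code meant for this study, and the note tells programmers to substitute it. V2.0 revised the appendix and still left the wrong label, and correcting it costs a few lines.

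Part of this stands. The misprints are on the page, and the numeric limits at the HbA1c positions cannot be what the authors intended. But the argument needs a point where a competent programmer would be left unsure which analysis is planned. The prose leaves no such doubt about arms, contrast, pooling or limits, and it governs over an example. Section 4.1 has any analysis before database lock run with dummy treatments, so a test run could expose a broken filter without unblinding anyone.

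Two further complaints carry little weight. The ridge prior is only something to be considered, so commenting it out contradicts nothing; its value is left open, but only inside the fallback. An upper limit of 1 on the treatment code, which Appendix 4 codes 1 and 2, has nothing to act on, because every randomized subject's arm is known.

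**Conclusion.** No change to the plan follows. The discrepancies are clerical slips in an example program whose governing text is correct. The label, naming and sort errors cannot silently alter the estimate. The limits in the fallback conflict with section 16.1.3, but the step is conditional and would touch perhaps 2 to 11 of 219 subjects under an assumed 1% to 5% rate of Week 12 gaps. Its behaviour in SAS is unknown. No effect on the Week 18 difference, its 95% interval or the comparison with 0.4% has been shown. This rests on the production program following section 16.1.3 where the example departs from it, which is how an analyst would ordinarily read the two together.

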APPENDIX 4. SAS CODE EXAMPLE FOR TIPPING POINT

```
/*An MNAR version of the MI procedure from Appendix 3 will be used.
The SHIFT value will start at 0.01 and be incremented until the critical
value for non-inferiority of 0.4 is surpassed. In particular, the upper limit
of the 95% confidence interval of the treatment difference will be calculated
for each iteration of the 0.01 increase to the MNAR adjustment and once it
surpasses 0.4, we take that MNAR adjustment value as k. */

/* The first part gives a monotone patern to the data */
/* It imputes the holes in the data but leave empty the missings at the */
/* end for discontinued patients */

Proc mi data= <<insert input dataset name>> out=datamono
  seed=20171220
  NIMPUTE=100;
  by trtp;
  var inv01 inv02 ... inv13 binstime HbA1c_BASE HbA1c_WK12 HbA1c_WK18;
  mcmc impute = monotone chain= multiple;
run;

/* This part gives the imputation at the end of data */
/* Experimental treatment is trtpn=2, control treatment is trtpn=1 */
/* The shifts are done on AVAL not the CHG therefore we subtract */
/* a positive shift to the control making it harder to obtain */
/* non-inferiority and at the same time add a positive shift to the */
/* experimental treatment */

proc sort data=datamono;
  by _imputation_;
run;
```

Document:	\sasdata\Mylan\Insulin_glargine\SYA22825\Biostatistics\Documentation\SAP\MYL-1501D-3004_SAP_Final_2_0_clean.doc		
Author:	[name]	Version Number:	2.0
		Version Date:	18OCT2018

Template No: CS_TP_BS016 Revision 4 Reference: CS_WI_BS005
Effective Date: 01Apr2016

Analysis Plan Template

```
proc mi data = datamono out = datamono2
    seed =20171220
    NIMPUTE=1;
by _imputation_;
    class trtpn strata sitegr1;
    monotone reg;
    MNAR    Adjust (<HbA1c_WK18>/SHIFT= +Kprime ADJUSTOBS=(trtpn='2'))
            Adjust (<HbA1c_WK18>/SHIFT= -Kprime ADJUSTOBS=(trtpn='1'));

    Var trtpn strata sitegr1 HbA1c_BASE HbA1c_WK12 HbA1c_WK18;
;
run;
```

Where Kprime is the shift value starting at 0.01 and ending at k.

```
proc mixed data= <<dataset>> method=REML order=internal;
    by shift_imputation_;
    class trtp(ref="Process V") strata sitegr1 avisit usubjid;
    model change= HbA1c_BASE trtp strata avisit sitegr1 trtp*avisit/DDFM=KR;
    repeated avisit/type=UN subject=usubjid;
    lsmeans trtp*avisit/diffcl;
run;
```

Document: \sasdata\Mylan\Insulin_glargine\SYA22825\Biostatistics\Documentation\SAP\MYL-1501D-3004_SAP_Final_2_0 clean.doc

Author: [name]

Version Number:

2.0

Version Date:

18OCT2018

Template No: CS_TP_BS016 Revision 4

Reference: CS_WI_BS005

Effective Date: 01Apr2016
